4.4 Withdrawal Criteria

The patient has the right to withdraw from the study at any time. Nevertheless, in this study, every attempt will be made to prevent missing data and to obtain complete follow-up of all patients.

Patients who meet study drug discontinuation criteria described in Sections 4.3 and 4.6 will be discontinued from study drug and may also be withdrawn from the study. However, patients who discontinue study drug are not required to withdraw from the study. As such, these patients will be encouraged to remain in the study and asked to attend all of the remaining study visits as outlined in the Schedule of Procedures in Appendix A. If a patient fails to actively maintain contact with the Investigator, reasonable efforts (telephone calls to family members or friends, email contacts, etc.) will be made in order to encourage the patient to complete the study visits.

If the patient withdraws from the study, the reason should be captured and could include the following:

- 1. The patient withdraws consent at any time or requests discontinuation from the study;
- 2. The patient fails to comply with protocol requirements or study-related procedures if, in the opinion of the Investigator or the Sponsor, the non-compliance will significantly compromise data interpretation or safety;
- 3. In the Investigator's judgment, it is in the patient's best interests;
- 4. Violation of the protocol inclusion and exclusion criteria is discovered, if, in the opinion of the Investigator or the Sponsor, the violation will significantly compromise data interpretation or safety; or
- 5. The Sponsor or the regulatory authority terminates the study.

Patients who choose to withdraw consent will be asked to document withdrawal of consent in writing.

Although a patient is not obligated to give his/her reason for withdrawing prematurely, the Investigator will make a reasonable effort to obtain the reason while fully respecting the patient's rights. The reason for withdrawal from the study must be documented in the eCRF. The Clinical Study Report will include the reason(s) for withdrawal from the study.

If a patient withdraws prematurely from the study, study staff will make every effort to complete the full panel of assessments scheduled for the Early Termination (ET) visit.

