6.6 Early Termination Visit and Withdrawal Procedures

The end of treatment for patients completing the study is Day 28. For patients who are withdrawn from the study prior to completion, all Day 28 procedures will be performed at an ET Visit. These procedures are outlined in the Schedule of Procedures in Appendix A.

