8.3 Serious Adverse Event Reporting – Procedures for Investigators

Initial Reports

All SAEs occurring from the time of informed consent until 30 days following the last administration of study drug must be reported to within 24 hours of the

knowledge of the occurrence. After the 30-day reporting window, any SAE that the Investigator considers related to study drug must be reported to the sponsor/designee.

To report the SAE, complete the SAE form electronically in the electronic data capture (EDC) system for the study. When the form is completed, personnel will be notified electronically by the EDC system and will retrieve the form. If the event meets serious criteria and it is not possible to access the EDC system, send an email to state at [contact] or call the state SAE reporting line (phone number listed below), and fax/email the completed paper SAE form to system becomes available, the SAE information must be entered as soon as possible of the system becoming available.

Follow-Up Reports

The Investigator must continue to follow the patient until the SAE has subsided or until the condition becomes chronic in nature, stabilizes (in the case of persistent impairment), or the patient dies.

Within 24 hours of receipt of follow-up information, the Investigator must update the SAE form electronically in the EDC system for the study and submit any supporting documentation (e.g., patient discharge summary or autopsy reports) to the procedures outlined above for initial reporting of SAEs.

8.4 **Pregnancy Reporting**

If a patient becomes pregnant from the time of initiation of study drug through the safety follow-up period defined in the protocol, the Investigator is to stop dosing with study drug immediately and the patient should be withdrawn from the study. ET procedures should be implemented at that time.

A pregnancy is not considered to be an AE or SAE; however, it must be reported to will then within 24 hours of knowledge of the event. Will then will then provide the Investigator/site the Exposure In Utero (EIU) form for completion. The Investigator/site must complete the EIU form and fax/email it back to within 24 hours of completion.

If the female partner of a male patient becomes pregnant while the patient is receiving study drug or within the safety follow-up period defined in the protocol, the Investigator should notify as described above.

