APPENDIX A: SCHEDULE OF PROCEDURES

Table 2. Schedule of Procedures

| | | Screening | Period | | | | | |
|-----------------------------------|-----------------------------------|----------------------|----------------------|--------------------------|------------------------|----------------|------------------|-------------------|
| | Screening Visit ^{a,b} | Qua | lification Per | Tr | Follow-Up Telephone | | | |
| Visit Name | Visit 1 | Visit 2 ^b | Visit 3 ^d | Visit 3.1 ^{d,e} | Visit 4 ^d | Visit 5 | Visit 6/ET | Call ^f |
| Study Day | -70 to -29 | -28 to -21 | -21 to -14 | - 14 to -7 | 1 | 14 | 28 | 35 |
| Visit Window (days) | | ±3 | ±3 | ±3 | | ±3 | ±3 | ±2 |
| Assessment | | | | | | | | |
| Informed consent ^g | Х | | | | | | | |
| Inclusion/exclusion criteria | Х | Х | Х | Х | Х | | | |
| Fasting TG level | | X ^h | X ^h | X ^h | | | | |
| | | | | | | | | |
| Serum FSH ⁱ | Х | | | | | | | |
| Pregnancy test ^j | Х | | | | X ^k | | X ^k | |
| Height, body weight, and BMI | Х | | | | | | X ^{k,1} | |
| Demographic/medical history | Х | | | | | | | |
| Urine drug screen ^m | Х | | | | | | | |
| Prior/concomitant medication | Х | Х | Х | Х | Х | Х | Х | Х |
| TSH, FT4, and HbA1c | Х | | | | | | | |
| Randomization | | | | | Xk | | | |
| Physical examination ⁿ | Х | | | | Xk | Xk | Xk | |
| Clinical laboratory tests° | Х | | | | Xk | Xk | Xk | |
| Vital signs ^p | Х | | | | Х | Х | Х | |
| 12-lead ECG ^q | Х | | | | Х | | Х | |
| PD sample ^r | Х | | | | X ^k | X ^k | X ^k | |
| Dispense study drug ^s | | | | | Х | | | |
| Dosing ^t | | | | | • | — x— | > | |
| AEs | • | | | X - | | | | |
| Study drug compliance check | | | | | | Х | Х | |

a. Patients who are screen failures for a modifiable condition, other than failing the TG criteria, can be re-screened once. Before each patient is re-screened, the Investigator should discuss the case with the Medical Monitor. Patients who are screen failures or run-in failures under Protocol Version 1.0 Inclusion 3 TG criteria may rescreen once with the review and approval of the Medical Monitor.

b. At the Screening Visit (Visit 1), patients not needing a washout period may start the Qualification Period 24 hours after signing the informed consent form. Patients may continue through the Qualification Period provided that there are no prohibitive safety or eligibility results from the Screening Visit (Visit 1) laboratory tests.

- c. All Qualification Period visits will occur 7 days (±3 days) apart.

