- d. The last fasting TG Qualification Period visit (Visit 3 or 3.1) should occur ≥ 7 days prior to Day 1 (Visit 4).
- e. For patients without a qualified medical record, Visit 3.1 is only needed if 1 Qualification Period TG level from Visit 2 or 3 is within 10% of the target range (≥135 mg/dL and <550 mg/dL) and 1 Qualification Period TG level from Visit 2 or 3 is within the target range (≥150 mg/dL).
- f. A Follow-Up Telephone Call will be performed 7 days (±2 days) following the last dose of study drug.
- g Written consent must be obtained from the patient prior to any study-specific procedure or investigation including the washout period when applicable

- i. FSH is to be obtained in women <55 years of age who have not had a menstrual period for ≥1 year. Female patients will be considered postmenopausal if the FSH level is in the central laboratory's normal range for postmenopausal phase.
- j. Female patients of childbearing potential must have a negative serum pregnancy test at the Screening Visit (Visit 1), a negative urine pregnancy test at Visit 4 and Visit 6, and must agree to use effective methods of contraception.
- k. Assessments will be performed prior to dosing.
- 1. Only body weight will be measured at Visit 6 prior to dosing.
- m. A urine drug screen will be performed at the discretion of the Investigator.
- n. At the Screening Visit, a complete physical examination excludes pelvic, rectal, and breast examinations. All other physical examinations throughout the study must include a symptom-directed physical examination, as well as an examination of the heart, lungs, and abdomen and a visual examination of the skin.
- o. Clinical laboratory tests will include hematology, serum chemistry, coagulation, and urinalysis.
- p. Vital signs include systolic and diastolic BP, pulse, respiratory rate, and body temperature and will be measured (sitting) after resting for a minimum of 5 minutes. Patients should avoid smoking, caffeine, or exercise within 30 minutes prior to BP measurement. On Days 1, 14, and 28, BP and pulse must be measured prior to administration of study drug and again approximately 1 hour post-administration.
- q. Patients must be supine for approximately 5 to 10 minutes before ECG collection and remain supine but awake during ECG collection.
- r. PD assessments will be performed under fasting conditions (≥8 hours) and include TG, TC, LDL-C, HDL-C, remnant cholesterol (calculated as TC LDL-C HDL-C), non-HDL-C, FFA.

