- s. Study drug, for entire treatment period, will be dispensed to eligible patients on Day 1 (Visit 4), after randomization, via the IRT system.
- t. Daily oral dose will be administered by the patient and taken according to treatment group starting on Day 1 (Visit 4) and concluding on Day 28 (Visit 6) (28 dosing days). Patients in the K-877-IR treatment group will receive only the morning dose on Day 28. Study drug will be administered in the fed state at 0 hour with 240 mL of room temperature tap water.
- AE = adverse event; = BMI = body mass index; BP = blood pressure; ECG = electrocardiogram; ET = Early Termination; FFA = free fatty acid;

FSH = follicle-stimulating hormone; FT4 = free thyroxine; HbA1c = hemoglobin A1c; HBsAG = hepatitis B surface antigen; HCV = hepatitis C virus; HDL-C = high-density lipoprotein cholesterol; HIV = human immunodeficiency virus; IRT = interactive response technology; LDL-C = low-density lipoprotein cholesterol; PD = pharmacodynamic(s); TC = total cholesterol; TG = triglyceride; TSH = thyroid-stimulating hormone.

Table 3. Schedule of Procedures

| | Screening Period | | | | | | | | | | | |
|-----------------------------------|-----------------------------------|-----------------------------------|-------------------------|-----------------------------|------------------|-------------------------|----------------|----------------|---------------|----------------|----------------|--------------------------------|
| | Screening Visit ^{a,b} | Qualification Period ^c | | | | Treatment Devied | | | | | | |
| | V ISIL ⁻³⁻² | | | Charle In | Treatment Period | | | | | | Follow-Up | |
| Visit Name | Visit 1 | Visit 2 ^b | Visit 3 ^d | Visit 3.1 ^{d,e} | Check-In 1 | Visit 4 ^d | Discharge 1 | Visit 5 | Check-In 2 | Visit 6/ET | Discharge 2 | Telephone Call ^f |
| | | -28 | -21 to | -14 to | | | | | | | | |
| Study Day | -70 to -29 | to -21 | -14 | -7 | -1 | 1 | 2 | 14 | 27 | 28 | 29 | 35 |
| Visit Window (days) | | ±3 | ±3 | ±3 | | | | ±3 | | ±3 | | ±2 |
| Assessment | | | | | | | | | | | | |
| Informed consent ^g | Х | | | | | | | | | | | |
| Inclusion/exclusion | | | | | | | | | | | | |
| criteria | х | Х | Х | Х | Х | Х | | | | | | |
| Fasting TG level | | X ^h | X ^h | X ^h | | | | | | | | |
| | | | | | | | | | | | | |
| | | | | | | | | | | | | |
| Serum FSH ⁱ | X | | | | | | | | | | | |
| Pregnancy test ^j | Х | | | | Х | | | | Х | | | |
| Height, body weight, | | | | | | | | | | | | |

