b. At the Screening Visit (Visit 1), patients not needing a washout period may start the Qualification Period 24 hours after signing the informed consent form. Patients may continue through the Qualification Period provided that there are no prohibitive safety or eligibility results from the Screening Visit (Visit 1) laboratory tests.

c. All Qualification Period visits will occur 7 days (±3 days) apart.

d. The last fasting TG Qualification Period visit (Visit 3 or 3.1) should occur ≥7 days prior to Day 1 (Visit 4).

e. For patients without a qualified medical record, Visit 3.1 is only needed if 1 Qualification Period TG level from Visit 2 or 3 is within 10% of the target range (\geq 135 mg/dL and <550 mg/dL) and 1 Qualification Period TG level from Visit 2 or 3 is within the target range (\geq 150 mg/dL and <500 mg/dL).

[figure not shown]
f. A Follow-Up Telephone Call will be performed 7 days (±2 days) following the last dose of study drug.

g. Written informed consent must be obtained from the patient prior to any study-specific procedure or investigation, including the washout period when applicable.

h.

- i. FSH is to be obtained in women <55 years of age who have not had a menstrual period for ≥1 year. Female patients will be considered postmenopausal if the FSH level is in the central laboratory's normal range for postmenopausal phase.
- j. Female patients of childbearing potential must have a negative serum pregnancy test at the Screening Visit (Visit 1), a negative urine pregnancy test at Check-Ins 1 and 2, and must agree to use effective methods of contraception.
- k. Only body weight will be measured at Visit 6 prior to dosing.
- 1. A urine drug screen will be performed at the discretion of the Investigator.
- m. Assessments will be performed prior to dosing.
- n. At the Screening Visit, a complete physical examination excludes pelvic, rectal, and breast examinations. All other physical examinations throughout the study must include a symptom-directed physical examination, as well as an examination of the heart, lungs, and abdomen and a visual examination of the skin.
- o. Clinical laboratory tests will include hematology, serum chemistry, coagulation, and urinalysis.

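### Protocol Table 3 leaves the pregnancy test out of its Visit 6/ET column, so a woman in the confined subset who withdraws before Check-In 2 has no scheduled test after her first dose

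*Protocol*

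**What the plan says.** Appendix A of the protocol gives two schedules. Table 2 covers patients who are not admitted. Table 3 covers the subset of 24 (of about 90) who stay at the site around Day 1 and Day 28; the name of this subset is blacked out.

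- **Table 2.** The end of treatment and early termination (ET) share one column: "Visit 5 | Visit 6/ET". The pregnancy-test row is marked at Visit 1, Visit 4 and Visit 6/ET. Footnote j asks for "a negative urine pregnancy test at Visit 4 and Visit 6", after a serum test at screening.
- **Table 3.** The readmission and the shared visit are separate columns: "Check-In 2 | Visit 6/ET | Discharge 2". The pregnancy-test row is marked at Visit 1, Check-In 1 (Day -1) and Check-In 2 (Day 27). Footnote j agrees: "a negative urine pregnancy test at Check-Ins 1 and 2". The Visit 6/ET cell is empty.
- **Section 6.6.** "For patients who are withdrawn from the study prior to completion, all Day 28 procedures will be performed at an ET Visit", with the procedures taken from Appendix A.
- **Section 4.4.** On premature withdrawal, staff try to complete "the full panel of assessments scheduled for the Early Termination (ET) visit".
- **Section 8.4.** The reporting duty opens with "If a patient becomes pregnant from the time of initiation of study drug through the safety" and runs to the end of safety follow-up. Reporting is due within 24 hours of knowledge, and the pregnancy is followed to its outcome where possible.

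SAP Tables 1 and 2 copy Protocol Tables 2 and 3 and carry the same difference.

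**The concern.** The content of the ET visit is defined only by reference to the Day 28 column of whichever schedule the patient follows. On one schedule that column contains a pregnancy test; on the other the end-of-treatment test sits a day earlier, in a column that an early leaver never reaches. For such a patient no pregnancy test is scheduled once dosing has begun. The duties in Section 8.4 start from knowledge of a pregnancy, so they depend on its being detected. What is at stake is a pregnancy exposed to study drug that goes unnoticed at exit.

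**Working it through.** No figure in the plan needs reproducing. The check is a cell-by-cell reading of the two rows, followed by tracing each type of patient.

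**Step 1: the pregnancy-test rows (protocol Appendix A)**

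| | Screening | Before first dose | End of treatment | Visit 6/ET cell |
|---|---|---|---|---|
| Table 2 | Visit 1 | Visit 4 (Day 1, before dosing) | Visit 6 (Day 28, before dosing) | marked |
| Table 3 | Visit 1 | Check-In 1 (Day -1) | Check-In 2 (Day 27) | blank |

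Row and footnote j agree within each table, and the SAP copies match. The blank is therefore not an effect of redaction or text extraction.

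**Step 2: the other rows.** Among the visible rows, the remaining assessments in Table 2's Visit 6/ET column also appear in Table 3's: body weight, concomitant medication, physical examination, laboratory tests, vital signs, ECG, PD sample and compliance check. Only the pregnancy test does not carry over.

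**Step 3: the ET rule.** Under Section 6.6, "all Day 28 procedures will be performed at an ET Visit". In Table 3 the test is a Day 27 procedure, so the rule does not bring it into the ET visit. Section 4.4 points to the same panel and adds nothing.

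**Step 4: who is affected**

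- Completers: tested on Day 28 (Table 2) or Day 27 (Table 3). No gap.
- Patients who stop study drug but stay in the study: Section 4.3 keeps them to Day 28, so on Table 3 they reach Check-In 2. No gap.
- Patients on Table 2 who withdraw and attend an ET visit: tested.
- Patients on Table 3 who withdraw before Check-In 2: last scheduled test on Day -1, none after the first dose.

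**Step 5: size.** The documents state neither a withdrawal rate nor the share of women of childbearing potential. An upper-end figure comes from treating the whole sample-size allowance (30 randomized for 26 needed per group) as early withdrawal:

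- Allowance: (30 − 26)/30 = 13.3%.
- In the subset: 24 × 4/30 = 3.2 patients.
- Assuming that 10% to 40% of these are women of childbearing potential: 3.2 × 0.10 = 0.3 to 3.2 × 0.40 = 1.3 patients.

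The true number is probably lower. The primary analysis uses the Per-Protocol Set, so the allowance must also absorb patients excluded for eligibility violations, stopping drug, prohibited medication or compliance outside 80% to 120%. None of these requires leaving the study.

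**The case against.** The strongest reply is that nothing here is a contradiction in the text. Table 3 is internally consistent, the two tables serve different patients, and Check-In 2 does for the admitted subset what Visit 6 does for the rest. Neither footnote j mentions early termination. A requirement to test at exit is inferred from the shared column heading together with Section 6.6, and the documents never name detection at exit as a purpose. There are also mitigations: contraception is required throughout the study, withdrawn patients are asked to attend an ET visit, a telephone call follows 7 days (±2) after the last dose, and an investigator may test at discretion.

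Much of this stands, and it limits the point to a narrow group. It does not close the gap. Section 6.6 does make the column heading operative, none of the mitigations is a scheduled test, and no visible passage gives a reason for treating the two groups differently at early termination.

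A reader might infer more than the documents support:

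- That admitted women have no end-of-treatment test at all. They do, on Day 27, about one day from the Table 2 timing.
- That anyone who stops study drug is missed. Section 4.3 keeps such patients in the study, although Section 4.4 allows that some may also be withdrawn.
- That about three patients would be affected. That figure takes the drop-off allowance as a withdrawal rate and ignores sex and childbearing potential.
- That a missed pregnancy is a serious adverse event in the protocol's terms. Section 8.4 says that a pregnancy is neither an AE nor an SAE, though it must be reported.

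**Conclusion.** The point holds in a narrow form. Followed as written, the two schedules differ at early termination, and a woman of childbearing potential in the 24-patient subset who withdraws before Check-In 2 has no scheduled pregnancy test after her first dose. Probably at most about one patient is affected. That size rests on the assumed 10% to 40% share and on an allowance that likely overstates withdrawal. The consequence is a possibly undetected exposed pregnancy. Sample size, power and the primary analysis are untouched. This is a minor safety-schedule correction.

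**What to change.** Reconcile the pregnancy-test row and footnote j of Protocol Table 3, and the same row and footnote in SAP Table 2, with Protocol Table 2 and Section 6.6, so that the pregnancy-test requirement at the ET visit is consistent across the two schedules. How the passages are brought into line is for the sponsor to decide.

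The cost is an edit to one table row and one footnote in the protocol and in its SAP copy. If the reconciliation leads to any extra tests, they would be at most a few urine tests of a kind that the trial already schedules in the Visit 6/ET column for the other patients (about 90 − 24 = 66).

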APPENDIX B: CLINICAL LABORATORY ANALYTES

Standard Safety Chemistry Panel

- Alanine aminotransferase Alkaline phosphatase Aspartate aminotransferase Blood urea nitrogen Chloride Creatinine Estimated glomerular filtration rate Glucose Lactate dehydrogenase Potassium Total bilirubin Uric acid
- Albumin Amylase Bicarbonate Calcium Creatine kinase Direct bilirubin Gamma-glutamyl transferase Inorganic phosphorus Lipase Sodium Total protein

# VERSION HISTORY

Version	Version Date	Description
1.0	21AUG2020	Original signed version
2.0	23NOV2020	SAP updated per Protocol Amendment v2.0

# LIST OF ABBREVIATIONS

Abbreviation	Definition
ADaM	Analysis Data Model
AE	Adverse event
ALP	Alanine Phosphatase
ALT	Alanine Aminotransferase
ANCOVA	Analysis of Covariance
AST	Aspartate Aminotransferase
ATC	Anatomical therapeutic chemical
BLQ	Below the limit of quantification
CDISC	Clinical Data Interchange Standards Consortium
CL	Confidence Interval
СК	Creatinine Kinase
COVID-19	Coronavirus Disease 2019
CRF	Case report form
CSR	Clinical Study Report
eGFR	Estimated Glomerular Filtration Rate
ECG	12-lead Electrocardiogram
FAS	Full Analysis Set
IRT	Interactive Response Technology
LLN	Lower limit of normal
LLOQ	Lower limit of quantification
MedDRA	Medical Dictionary for Regulatory Activities
PPS	Per-Protocol Set

Abbreviation	Definition
SAE	Serious adverse event
SAP	Statistical Analysis Plan
SD	Standard deviation
SDTM	Study Data Tabulation Model
TEAE	Treatment-emergent adverse event
TESAE	Treatment-emergent serious adverse event
TG	Triglyceride
ULN	Upper limit of normal
WHO	World Health Organization

